11.3 INCIDENCE OF REDUCED LEAFLET MOTION IN SUBJECTS IN WHICH IT WAS PREVIOUSLY

Incidence of reduced leaflet motion up to 1 year post-implant will be evaluated, as described for the sensitivity analysis 1 of the primary endpoint (Table 3), selecting only subjects in which reduced leaflet motion was detected during the first CT scan (Table 3, scenarios n. 3 and 4).

A shift table will be displayed, for each Core Lab parameter defined in Section 10.3, to evaluate the changes in the imaging evaluation by Core Lab, between the first and second CT scans.

This analysis will be repeated by subgroup defined in Section 5.3.

11.4 INCIDENCE AND RELATIONSHIP OF REDUCED LEAFLET MOTION TO THE DEVICES, PROCEDURE, OR OTHER CAUSES

Study: APR002 BELIEVE

Incidence and its 90% CI, of reduced leaflet motion up to 1 year post-implant will be calculated (by overall and in subgroup defined in Section 5.3) in the following categories (reference category is underlined):

- Labeled valve size implanted [S/M/L/XL]
- Surgical procedure:
 - Approach [minimal invasive (mini-thoracotomy or mini-sternotomy)/full sternotomy]
 - Minimal invasive approach (mini-thoracotomy/mini-sternotomy)
 - Abnormality of ascending aorta or aortic root [Yes/No]
- Previous cardiovascular procedures [Yes/No]
- Subject risk factors:
 - Cardiac risk factor [Yes/No]
 - Yes if at least one of the following is marked: systemic hypertension; coronary artery disease; angina; myocardial infarction; heart failure; carotid artery disease; PTCA; stroke; TIA; endocarditis.
 - Vascular or pulmonary risk factors [Yes/No]
 Yes if at least one of the following is marked: peripheral vascular disease; pulmonary hypertension; chronic lung disease.
 - Diabetes [Yes (mellitus type I or II/No]
 - Dyslipidemia [Yes/No]
 - Neoplasia [Yes (Life expectancy more or less than 1 year) /No]
 - Tobacco user [Yes (current or former)/No]

A forest plot will be used to graphically represent the estimate point of the incidence together with its 90% CI in each category; number of subject with reduced leaflet motion and number of total subject in each category will be also displayed.

Logistic models (Walker and Duncan 1967, Cox 1958) will be run to evaluate the univariate (one by one) association between reduced leaflet motion and each category listed above including the subgroup defined in Section 5.3: concomitant procedures [refers to "without"], subject symptoms [refers to "asymptomatic"], ACT/DATP [refers to "off"], Core Lab evaluation [refers to "TEE"]. Coefficient regression estimates, by referring to the underlined sub-categories, will be provided together with its 90% CI.

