6.3.6. STUDY ENDPOINTS DEFINITIONS AND ASSESSMENTS

The primary endpoint will be evaluated with statistical hypothesis tests formally defined in Section 10.

Primary endpoint

The primary endpoint is the incidence of reduced leaflet motion identified through 4D volume-rendered CT imaging at minimum 1 month after the end of the anticoagulation or dual antiplatelet therapy (expected within 1 to 6 months post-implant, preferably 3 months), as assessed by an independent Core Lab. Enrolled subjects not receiving anticoagulation or antiplatelet therapy at discharge will be assessed via 4D volume-rendered CT imaging at a minimum of 30 days after hospital discharge.

• Secondary endpoints

The secondary endpoints are as follows:

- 1. Incidence of reduced leaflet motion (thrombus) with subanalysis in symptomatic and asymptomatic subjects, based on CT outcomes, and anticoagulation and dual antiplatelet treatment modalities, up to 1 year post-implant.
- 2. Incidence of reduced leaflet motion on 2nd 4D volume-rendered CT scan with contrast up to 1 year post-implant, in subjects in which reduced leaflet motion was previously detected.
- 3. Incidence and relationship of reduced leaflet motion to the device, procedure, or other causes up to 1 year post-implant.
- 4. Freedom from valve safety events (all-cause mortality, valve reintervention, myocardial infarction, structural valve deterioration, moderate or severe valve regurgitation, valve endocarditis, valve thrombosis, thromboembolic events, hemolysis and major bleeding) up to 1 year postimplant.
- 5. NYHA classification at 1 year post-implant.
- 6. Hemodynamic performance up to 1 year post-implant through TTE assessed by Echocardiographic Core Lab.

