7.10. VISIT WINDOW GUIDE

Visit Name	Calculate from:	Window Start Day	Window Stop Day
Pre-Implant / Implant Data	Enrollment date	- 90	0
Hospital Discharge (completed prior to actual discharge)	Implant date	0	30
ACT / DAPT Discontinuation or Planning Visit	Implant date 90 days after Implant date preferred	30	180
1 st CT-scan Follow-up Visit (no ACT/DAPT)	Hospital Discharge date 30 days after Hospital Discharge preferred	30	90
1 st CT-scan Follow-up Visit (DC on ACT/DAPT)	ACT / DAPT Discontinuation date	60	240
2 nd CT-scan (if needed) A minimum of 6 weeks after 1 st CT-scan	Implant date	180	300
1 year follow-up	Implant date	335	395

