10.5 SENSITIVITY ANALYSES

The analysis of the primary endpoints, which will provide incidence of reduced leaflet motion and its 90% CI, will be assessed in sensitivity analyses using different assumptions and populations (in each case, the same estimate and 90% CI calculation as specified in previous Section 10.4 will be applied):

COPYRIGHT LIVANOVA. ALL RIGHTS RESERVED. MAY NOT BE REPRODUCED WITHOUT PERMISSION. ALL HARD COPIES SHOULD BE CHECKED AGAINST THE CURRENT ELECTRONIC VERSION WITHIN MASTERCONTROL PRIOR TO USE AND DESTROYED PROMPTLY THEREAFTER. ALL HARD COPIES ARE CONSIDERED UNCONTROLLED DOCUMENTS.

LN-GLB-CLN-TEM-0033 rev1 Page 17 of 42

• Sensitivity Analysis 1: using the rationale to define the presence/absence of reduced leaflet motion as described in Table 3.

Study: APR002 BELIEVE

Table 3: Use of CT scan results to define incidence in the primary sensitivity analysis

Scenario #	Reduced leaflet motion at first CT scan	Reduced leaflet motion at second CT scan	Sensitivity Analysis 1
1	No	No	No Reduction
2	No	Yes	Reduction
3	Yes	No	No Reduction
4	Yes	Yes	Reduction

If the first CT scan showed no signs of reduced leaflet motion (scenario 1 and 2), a repeat exam is not mandated and will only be done if it becomes clinically indicated.

If no second CT scan will be performed, reduction/not reduction will be assigned as in Table 2.

- Sensitivity Analysis 2: using the PP population by excluding subject with major primary endpoint-related protocol deviations as described in Section 6.4.
- Sensitivity Analysis 3: Multiple Imputation (MI) analysis to adjust the primary analysis for the uncertainty introduced by the missing observations at first CT scan visit.

The objective of the MI (sensitivity analysis 3) is to impute reduction or no reduction for all subjects with missing values at first CT scan visit, and to perform this multiple time, so that the uncertainty or the imputation can be correctly accounted for in the analysis. Subject with missing data at first CT scan visit will have their missing value imputed according to *Missing At Random* assumptions and taking into consideration specific baseline characteristics.

The following steps will be carried out for the MI of missing data at first CT scan visit for the SAF set:

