11 SECONDARY EFFICACY ANALYSES

11.1 SECONDARY EFFICACY ENDPOINTS

The secondary efficacy endpoints for the study will be evaluated in the SAF and are:

- Incidence of reduced leaflet motion (thrombus) with subanalysis in symptomatic and asymptomatic subjects based on CT outcomes and ACT/DAPT modalities up to 1 year postimplant.
- Incidence of reduced leaflet motion on second 4D CT scan with contrast up to 1 year postimplant, in subjects in which reduced leaflet motion was previously detected.
- Incidence and relationship of reduced leaflet motion to the devices, procedure, or other causes up to 1 year post-implant.
- Freedom from valve safety events (all-cause mortality, valve re-intervention, myocardial
 infarction, structural valve deterioration, moderate or severe valve regurgitation, valve
 endocarditis, valve thrombosis, thromboembolic events, hemolysis and major bleeding) up
 to 1 year post-implant.
- NYHA classification at 1 year post-implant.

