18.5 HANDLING OF MISSING VALUES

At each time point/visit, all subjects still in the study are reported. Missing values will be taken into account as missing in the analysis. The number of observed values and the number of missing values must sum up to the number of subjects in the study at the respective time point/visit.

Missing measurements/missing values are identified by the SDTM variable **STAT=ND. If this variable is not recorded (it's a permissible variable) the missing values of **ORRES should be used.

Unless otherwise specified in the SAP, missing values will not be imputed. If missing values are imputed, the result of all imputation strategies and newly derived information must be stored

COPYRIGHT LIVANOVA. ALL RIGHTS RESERVED. MAY NOT BE REPRODUCED WITHOUT PERMISSION. ALL HARD COPIES SHOULD BE CHECKED AGAINST THE CURRENT ELECTRONIC VERSION WITHIN MASTERCONTROL PRIOR TO USE AND DESTROYED PROMPTLY THEREAFTER. ALL HARD COPIES ARE CONSIDERED UNCONTROLLED DOCUMENTS.

in the ADaM data set. The shifts required for the shift tables should already be included in the ADaM data set.

Study: APR002 BELIEVE

Imputed values will be listed in the subject data listing and be marked as imputed.

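### SAP 11.3 borrows a first-scan fallback for the second-scan endpoint without stating a denominator; read literally, first-scan positives who are not rescanned count as persistent reduced motion

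*SAP*

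**What the plan says.** Protocol 6.3.6 defines secondary endpoint 2 as "Incidence of reduced leaflet motion on 2nd 4D volume-rendered CT scan with contrast up to 1 year post-implant", in subjects in whom reduced motion had already been detected. SAP 11.1 keeps this: "Incidence of reduced leaflet motion on second 4D CT scan with contrast up to 1 year postimplant". In both, the outcome is read on the second scan.

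SAP 11.3 says that the endpoint "will be evaluated, as described for the sensitivity analysis 1 of the primary endpoint (Table 3", and restricts it by "selecting only subjects in which reduced leaflet motion was detected during the first CT scan (Table 3, scenarios n. 3 and 4". Sensitivity Analysis 1 (SAP 10.5) classifies subjects from both scans using Table 3, and adds: "If no second CT scan will be performed, reduction/not reduction will be assigned as in Table 2". In Table 2 (SAP 10.3) a positive first scan is *Reduction*. The general rule in SAP 18.5 is "Unless otherwise specified in the SAP, missing values will not be imputed".

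On timing:

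- Protocol 7.8 and SAP 5.4 place the second scan after the first and before the 1-year visit, with 6 to 10 months as the expected time.
- The window guide (Protocol 7.10, repeated in SAP 18.6) gives day 180 to 300 after implant, with the note "A minimum of 6 weeks after 1 st CT-scan". The summary list in SAP 18.6 gives 6 to 10 months.
- For the ACT/DAPT discontinuation or planning visit, the guide reads "90 days after Implant date preferred 30 180", that is, day 30 to 180 after implant.
- For subjects discharged on ACT/DAPT, the guide puts the first CT 60 to 240 days after discontinuation. The schedule table (Protocol 8.1) and SAP 5.4 and 18.6 give 30 days plus a 60-day window.

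**The concern.** The endpoint asks whether reduced motion found once is still there later. The fallback answers for subjects nobody looked at again, and within this endpoint it can give only one answer. Death, explant, withdrawal or a missed visit before the second scan would each enter as persistent reduced motion. The exact interval would also count these subjects as observed, so it would tend to look more precise than the data allow.

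Few positives are likely, so one or two such subjects matter. Two competent programmers could also follow SAP 11.3 and report different proportions. The shift table required in the same section rests on actual second-scan readings, so it need not agree with the headline figure.

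**Working it through.** **1. The plan's own figures.** Neither document gives a figure for this endpoint. The figures they do give reproduce:

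- Enrollment: 75 / (1 − 0.15) = 88.2, against a stated figure of approximately 88.
- Precision: the exact (Clopper-Pearson) 90% interval for 7/75 = 9.3% is 4.46% to 16.82%, a width of 12.35 points. At a proportion of 10% the width is 12.69 points. Both are below the stated 13.

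**2. How many positives.** Protocol 2.1 cites 8–12% reduced motion after SAVR. On 75 scans that is 0.08 × 75 = 6 to 0.12 × 75 = 9. I assume 8.

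**3. Direction of the effect.** Let n positives be rescanned, x of them still reduced, and m not rescanned.

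- Second scans only: x/n.
- With the fallback: (x + m)/(n + m).
- Difference: m(n − x) / [n(n + m)].

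This is never negative. It is zero only if nobody is missing or every rescanned subject is still reduced.

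**4. Size, for 8 positives** (all counts assumed; exact 90% CIs):

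| Rescanned | Still reduced | Second scans only | With fallback |
|---|---|---|---|
| 7 | 3 | 3/7 = 43% (13–78%) | 4/8 = 50% (19–81%) |
| 5 | 2 | 2/5 = 40% (8–81%) | 5/8 = 63% (29–89%) |
| 5 | 0 | 0/5 = 0% (0–45%) | 3/8 = 38% (11–71%) |

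Check on row 2: 3 × (5 − 2) / (5 × 8) = 9/40 = 22.5 points, and 62.5 − 40 = 22.5.

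**5. Timing.** Take discontinuation within the day 30–180 visit window. Six weeks is 42 days, and 300 − 42 = 258, so a first CT after day 258 leaves no second-CT date inside the guide's window.

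- First CT 30–90 days after discontinuation: the latest is 180 + 90 = day 270, and 270 + 42 = 312 > 300. The conflict needs discontinuation after day 258 − 90 = 168 and a late scan, which is 78 of 151 × 61 = 9,211 allowed day combinations (0.8%).
- First CT 60–240 days after discontinuation, as the guide prints: the latest is 180 + 240 = day 420. The conflict covers 48% of allowed day combinations.
- If 60–240 were counted from implant: 240 + 42 = 282, so no conflict.
- Discharged off ACT/DAPT: the latest first CT is 30 + 90 = day 120, and 120 + 42 = 162, so no conflict.

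These shares count calendar combinations. They do not forecast subjects.

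**The case against.** The best defence is that SAP 11.3 cites scenarios 3 and 4, and both rows of Table 3 contain an actual second-scan result. A subject with no second scan fits neither row. The fallback sentence directly follows the remark that first-scan negatives need no repeat exam, which is its natural use; for positives the second scan is required. SAP 5.2 makes non-missing subjects the default denominator, and SAP 18.5 makes non-imputation the default. All this supports a restriction to rescanned subjects and rules out claiming that the SAP certainly counts unscanned positives as persistent. It does not settle the matter. Both defaults give way where the SAP specifies otherwise, the fallback is such a specification, and SAP 11.3 imports the method that contains it.

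A reader might also infer that a second scan after day 300 would be discarded and the subject returned to *Reduction*, because SAP 18.6 assigns measurements by window. The documents do not support that. The fallback applies only when no second scan is performed, and a late scan was performed. SAP 18.6 refers back to SAP 5.4, where 6 to 10 months is an expectation and the limit is the 1-year visit.

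Nor do the windows show that missing second scans are built into the schedule. On the 30–90 day reading the clash is rare. Discontinuation is preferred at day 90, and the first CT is expected at 1 to 6 months.

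Finally, three unscanned of eight has no source in the documents. Planned attrition is 15%, and TEE may replace CT. The row with one unscanned subject, 43% against 50%, is the milder case.

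**Conclusion.** The denominator defect stands. SAP 11.3 defines a second-scan endpoint by a method that, taken literally, fills in missing second scans with the one answer that signals persistence, and it does not say whether that part of the method applies. The direction of the effect is certain if the fallback is used. The size depends on how many positives go unscanned: about 7 points with one of eight missing and about 23 points with three of eight, on the assumed outcomes. It disappears if all positives are rescanned or all those rescanned are still reduced.

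This is a secondary endpoint in a descriptive study, and the primary estimate is untouched. The timing part is an inconsistency between passages. It is marginal or large according to which first-CT window was meant, and it is not evidence that valid second scans would be lost.

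**What to change.** In SAP 11.3:

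- Set the denominator to first-scan positives with an evaluable second scan, by CT or substitute TEE.
- State that the Table 2 fallback of Sensitivity Analysis 1 does not apply to this endpoint.
- Report the number of first-scan positives not rescanned. Bounds with all of them persistent and all of them resolved are optional.

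In SAP 18.6, say that for analysis the definition in SAP 5.4 governs, so that a second scan performed outside day 180–300 is used.

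The timing passages must also be reconciled: SAP 5.4 and Protocol 7.8 with the second-scan row of the window guide and the list in SAP 18.6, and the two first-CT windows with each other. Which visit windows are right is for the sponsor to decide.

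The analysis changes need only SAP wording, with no new visits or data. The price is a smaller denominator and, as a rule, a wider interval: 8–81% instead of 29–89% in the second row of the table, or 73 points instead of 60.

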11.5 Freedom from Valve Safety

The following mortality and morbidity outcomes will be analyzed by means of time to event methods:

all-cause mortality

COPYRIGHT LIVANOVA. ALL RIGHTS RESERVED. MAY NOT BE REPRODUCED WITHOUT PERMISSION. ALL HARD COPIES SHOULD BE CHECKED AGAINST THE CURRENT ELECTRONIC VERSION WITHIN MASTERCONTROL PRIOR TO USE AND DESTROYED PROMPTLY THEREAFTER. ALL HARD COPIES ARE CONSIDERED UNCONTROLLED DOCUMENTS.

LN-GLB-CLN-TEM-0033 rev1 Page 21 of 42

- valve re-intervention
- myocardial infarction
- structural valve deterioration
- moderate or severe valve regurgitation
- valve endocarditis
- valve thrombosis
- thromboembolic events
- hemolysis
- major bleeding
- pacemaker implantation

Cox's proportional hazards regression models (Cox 1972, Breslow 1975) will be performed including, one by one, the following covariates: age class [refers to "≥18 and <65" years], gender [refers to "male"], ethnicity [refers to "not Hispanic or Latino"], presence of subject risk factor at baseline [refers to "No"], , NYHA at baseline [refers to "Class I"], abnormality of ascending aorta or of aortic root at implant [refers to "No"], presence of aortic regurgitation measured by post-implant intraoperative TEE [refers to "No"], reduced leaflet motion at first CT scan [refers to "No"], including the subgroup defined in Section 5.3: concomitant procedures [refers to "without"], subject symptoms [refers to "asymptomatic"], ACT/DATP [refers to "off"], Core Lab evaluation [refers to "TEE"].

Study: APR002 BELIEVE

Hazard rate, and its 90% CI, will be reported for each covariate.

Proportional hazard assumption will be investigated for each time-dependent outcome. In case of non-proportional hazards, a Weibull model will be assumed as parametric form of the distribution of survival times.

An additional analysis will be performed in order to evaluate the time free from ACT/DAPT to primary endpoint (reduced leaflet motion) up 1 year post-implant. Kaplan-Meier estimates and plots of time to event after implant will be produced as in Section 5.2. Subjects will be included in the analysis starting from their stop date of ACT/DAPT until the first evaluation of leaflet motion.

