6.3.3. EXCLUSION CRITERIA

Subjects who meet any of the following criteria will be excluded:

- The subject has a planned concomitant cardiac surgical procedure (other than CABG or septal myectomy) including MAZE procedures, atrial fibrillation surgery, and left atrial appendage exclusion or resection, or has a prosthesis in any other valvular position.
- 2. The subject has any medical condition requiring long term anticoagulation or dual antiplatelet therapy.
- 3. The subject has any clinical condition precluding the use of CT imaging with contrast.
- 4. The subject had a stroke or myocardial infarction (STEMI and NSTEMI) within 30 days prior to the planned valve implant surgery.
- 5. The subject has active endocarditis, myocarditis, or sepsis.
- 6. The subject is in cardiogenic shock manifested by low cardiac output and needing hemodynamic support.
- 7. The subject is already included in another clinical study that could confound the results of this clinical investigation.

The PI shall be responsible for ensuring all potential subjects meet the inclusion/exclusion criteria and are an appropriate subject for this clinical study.

Individuals who are screened but do not satisfy the inclusion and exclusion criteria will not be considered for enrollment in the study. Logs will be maintained for screening and consenting subjects.

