5.2 DESCRIPTIVE STATISTICS

Descriptive statistics will be calculated using as reference the number of subjects in the relevant analysis population (any exception will be specified) according to the nature of the data as follows:

Study: APR002 BELIEVE

- Continuous variables: number of non-missing observations, arithmetic mean, standard deviation, minimum and maximum values, median and quartiles.
 - If there are less than 5 observations, only the number of non-missing observations, arithmetic mean, median, minimum and maximum will be presented.
- Categorical variables: number of non-missing observations (n), the number of missing and the relevant percentage on the analysis population, number and relative frequencies. If not defined otherwise, the percentage denominator will be the number of subjects with nonmissing information.
 - In case of subcategories, the relative frequencies will be calculated based on the subjects in the subcategory, in this case a footnote will be added explaining the different denominators.
- Time-to-event variables: number of non-missing observations (n), minimum, first quartile, median including 90% CI, third quartile, and maximum. For calculating the survival estimate 90% CI bounds the log-log transformed estimate of CI bounds will be used. Greenwood formula will be used to estimate the variance of the log-log transformation of the Kaplan-Maier estimator.

In addition, Kaplan-Meier estimates and plots will be provided with:

- o the respective number at risk and the Kaplan-Meier estimates at time points 1 month, 3 months, 6 months, 9 months and 1 year.
- o the median and its 90% Cl.
- o the Hazard Ratio (HR), its 90% CI and the relevant p-value, when applicable.

Subjects ongoing and who are free from event at the analysis cut-off date will be censored at the analysis cut-off date. Subjects who have discontinued without an event will be censored at the date of discontinuation.

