6.3 SAFETY ANALYSIS POPULATION

The "Safety" population (SAF) is defined as all enrolled subjects successfully implanted with one of the study aortic heart valves. The SAF population will coincide with the ENR population and will be used for efficacy, performance and safety summaries.

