8.4 Medical History and Previous Cardiovascular Procedures

Medical history will be analyzed by means of summary statistics. It includes but it is not limited to history of systemic hypertension, coronary artery disease, angina, myocardial infarction, heart failure, carotid artery disease previous carotid artery intervention or percutaneous transluminal carotid angioplasty (PTCA), transient ischemic attack (TIA), stroke, endocarditis, peripheral vascular disease, pulmonary hypertension, chronic lung disease, diabetes, dyslipidemia, neoplasia, tobacco user.

Previous cardiovascular procedures will be summarized descriptively, as appropriate: coronary artery bypass surgery (CABG) and specifications, percutaneous coronary intervention, arrhythmia procedure and specifications, pulse generator implant and specifications, revision of the Aortic Valve Replacement Surgery and specification, STS predicted risk of mortality [%], where applicable. Details for "other arrhythmia procedure" and year of intervention/implants will be presented in a listing, if applicable.

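### SAP 11.5 does not limit the pacemaker analysis to subjects without a pacing device at surgery, so the estimated risk of a first pacemaker may be slightly too low (minor).

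*SAP*

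**What the plan says.** SAP 11.5 opens with "The following mortality and morbidity outcomes will be analyzed by means of time to event methods" and gives eleven outcomes, the last being "pacemaker implantation". Each gets Kaplan-Meier estimates under SAP 5.2 and Cox models with one covariate at a time.

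The population is the full safety set (SAF). Table 1 in SAP 6.5 assigns the secondary efficacy analyses to it, and SAP 6.3 says "The SAF population will coincide with the ENR population and will be used for efficacy, performance and safety summaries". SAP 11.1 names the same population ("The secondary efficacy endpoints for the study will be evaluated in the SAF and are"), although the list it introduces omits pacemaker implantation, so Table 1 is the firmer support. For descriptive statistics SAP 5.2 states the default: "Descriptive statistics will be calculated using as reference the number of subjects in the relevant analysis population (any exception will be specified"). No exception is specified for this outcome.

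The seven criteria in Protocol 6.3.3, headed "Subjects who meet any of the following criteria will be excluded", do not mention a previous pacemaker or other pulse generator. SAP 8.4 provides for such subjects, because it summarises "pulse generator implant and specifications" as a previous cardiovascular procedure.

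The censoring rules in SAP 5.2 and 18.13 cover event-free subjects who are ongoing or have discontinued. They do not address a subject who was never at risk.

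**The concern.** A risk set should contain only subjects who can have the event. Someone who has a pacemaker at valve surgery cannot receive a first one, yet under the SAP that person counts as event-free from the day of implant to the end of follow-up. If such subjects enrol, the curve for freedom from a first pacemaker lies too high. For that reading of the event the error goes one way only, in favour of the device. At stake is how closely one reported safety figure matches what a reader will take it to mean: the risk of needing a pacemaker after this valve among patients who did not have one.

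**Working it through.** **Inputs from the documents.** Planned enrolment is about 88 (SAP 2.3: 75 evaluable scans, 15% attrition), and 75 / 0.85 = 88.2 agrees. Intervals are two-sided 90% (SAP 5.1). Follow-up is 1 year. The documents state no figure for pacemaker implantation, so there is no planned value to reproduce.

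**Inputs assumed.** The share of subjects with a pacing device at baseline (2% to 15%), the one-year rate among those at risk (5% to 20%), and the event counts in the examples. None of these has a source in the documents.

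**Formula.** Let N be the size of the SAF, k the number with a device at baseline and r the one-year risk among the N − k others. If carriers cannot have the event and censoring does not differ between the two groups:

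- risk in the whole SAF = r × (N − k) / N
- relative understatement = k / N
- absolute understatement = r × k / N

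**Range at N = 88**, using simple proportions without censoring:

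| Assumed share | k | (88 − k) / 88 | Shortfall, r = 5% | r = 10% | r = 20% |
|---|---|---|---|---|---|
| 2% | 2 | 0.977 | 0.11 points | 0.23 | 0.45 |
| 5% | 4 | 0.955 | 0.23 | 0.45 | 0.91 |
| 10% | 9 | 0.898 | 0.51 | 1.02 | 2.05 |
| 15% | 13 | 0.852 | 0.74 | 1.48 | 2.95 |

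The corners of the table are 2/88 × 5% = 0.11 points and 13/88 × 20% = 2.95 points.

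**Against the sampling error.** Take 9 first implants as an example, with exact (Clopper-Pearson) 90% limits:

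- Whole SAF: 9/88 = 10.2% (5.4% to 17.2%)
- k = 2: 9/86 = 10.5% (5.6% to 17.6%)
- k = 4: 9/84 = 10.7% (5.7% to 18.0%)
- k = 9: 9/79 = 11.4% (6.1% to 19.0%)
- k = 13: 9/75 = 12.0% (6.4% to 20.0%)

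The estimate moves by 0.2 to 1.8 points, while the whole-SAF interval is about 12 points wide. At the extreme corner (k = 13, r = 20%, hence 15 events), 15/88 = 17.0% (10.8% to 25.0%) compares with 15/75 = 20.0%: a shift of 3.0 points against a width of about 14.

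**The case against.** The strongest reply is that freedom from pacemaker implantation among all implanted subjects is a coherent descriptive quantity and follows the SAP's own population rule. The outcome is not labelled as a first or new pacemaker, and the content of the protocol's definitions appendix is not in the text available here. If a generator replacement counted, carriers could have an event. It is also not shown that any carrier will enrol. Previous pulse generators will be tabulated and all data listed, so a reader could make an approximate correction by division. The study is descriptive, and no decision depends on a pacemaker threshold.

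Much of this stands. It makes the point conditional and limits its weight. It does not remove it: if replacements counted, the figure would mix two kinds of event, so the definition and the risk set need stating either way. An after-the-fact division also does not correct the Kaplan-Meier curve, its interval or the Cox models.

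Two stronger readings are tempting. One is that the new-pacemaker rate is certainly understated. The documents do not support this, because they give neither the event definition nor a count of carriers. The other is that the hazard ratios for age and NYHA class are biased in a known direction. The documents report no association between those covariates and a previous device, and the direction would depend on which level of the covariate held more carriers.

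The baseline field also records pulse generators, which may be a wider category than pacemakers. Its specifications are needed before anyone is removed from the risk set.

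**Conclusion.** The concern holds in conditional form. As written, the SAP keeps subjects with a pre-existing pacing device in the risk set for pacemaker implantation. If the event means a first pacemaker and at least one such subject enrols, the cumulative risk is understated in relative terms by about their share of the SAF. Under the assumptions above this is 2% to 15% relative, or 0.1 to 3.0 percentage points, and well inside the sampling error at about 88 subjects. With no carriers it is zero.

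The effect is confined to one secondary safety outcome that SAP 11.5 adds. The outcome appears in neither the endpoints of Protocol 6.3.6 nor the list in SAP 11.1. The primary endpoint and the sample size are untouched. Severity: minor.

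**What to change.** In SAP 11.5:

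1. Define the event as the first pacemaker implantation after valve implant.
2. Restrict the risk set for this outcome, in both the Kaplan-Meier and Cox analyses, to subjects with no pacing device at baseline. Identify them from the pulse generator field in SAP 8.4, and use its specifications to state which device types lead to removal.
3. Report the number left out and the resulting denominator.
4. Show the whole-SAF estimate beside the restricted one.

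This takes a few lines of SAP text and one programming filter on a field already collected. The downside is a slightly smaller denominator, so a slightly wider interval, and a slightly less favourable figure.
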